# 7.4 Total number of samples and blood withdrawn

During the study the following volume of blood will be collected:

For routine laboratories analysis:

Screening visit: 12.5 mL Final visit/ETV: 12.5 mL

For PK analysis:

Treatment T: 15x2x7=210 mL Treatment R: 15x2x7=210 mL

In total, 445 mL of blood (not exceeding a normal blood donation) will be withdrawn from each subject.

# 8 ASSIGNMENT OF STUDY TREATMENT

#### 8.1 Randomisation

The randomisation list will be computer-generated by the Biometry Unit of the Clinical Contract Research Organization (CRO), using the PLAN procedure of the SAS® version 9.3 (TS1M1) (13) or higher (the actual version will be stated in the final report). The randomisation list will be supplied to the study site and to STM Pharma PRO Srl., Italy (§ 16.5) for the preparation of the IMP individual kits before study start and will be attached to the final clinical study report.

#### **8.2** Treatment allocation

The study subjects will be assigned to one of 2 sequences of treatments (either RTRT or TRTR) according to their randomisation number. Randomisation number will be given to the subjects on study Day -1, period 1, as soon as they are definitely enrolled in the study.

## 8.3 Blinding

This is an open study. No masking procedure will be applied.

# 9 EVALUATION PARAMETERS

## 9.1 Study variables

## 9.1.1 Primary variables

> Cmax and AUC0-t of plasma riluzole after replicate single dose administration of test and reference formulation.

## 9.1.2 Secondary variables

- $ightharpoonup AUC_{0-\infty}$ ,  $t_{1/2}$ ,  $t_{max}$ ,  $AUC_{extra}$ ,  $\lambda_{z_{s}}$  of riluzole after replicate single dose administration of test and reference;
- Palatability score
- > TEAEs, vital signs (BP, HR), laboratory parameters, physical examination including BW

#### 9.2 Pharmacokinetic assessments

## 9.2.1 Pharmacokinetic parameters

The following PK parameters will be measured and/or calculated for plasma riluzole, using the validated software Phoenix WinNonlin® version 6.3 (12) or higher (actual version will be stated in the final report):

Cmax: Maximum plasma concentration

 $t_{max}$ : Time to achieve  $C_{max}$ 

 $\lambda_z$ : Terminal elimination rate constant, calculated, if feasible, by log-linear

regression using at least 3 points

 $t_{1/2}$ : Half-life, calculated, if feasible, as  $ln2/\lambda_z$ 

AUC0-t: Area under the concentration-time curve from administration to the last

observed concentration time t, calculated with the linear trapezoidal method

 $AUC_{0-\infty}$ : Area under the concentration-time curve extrapolated to infinity, calculated, if

feasible, as  $AUC_{0-t} + C_t/\lambda_z$ , where  $C_t$  is the last measurable drug concentration

%AUCextra: Percentage of the residual area  $(C_t/\lambda_z)$  extrapolated to infinity in relation to

the total AUC0- $\infty$ , calculated, if feasible, as  $100 \times [(C_t/\lambda_z)/AUC_{0-\infty}]$ 

The sampling schedule is considered adequate if the ratio  $AUC_{0-t}/AUC_{0-\infty}$  equals or exceeds a factor of 0.8 (i.e. if %AUCextra is <20%) for more than 80% of the individual PK profiles. This assures that the primary variable  $AUC_{0-t}$  covers a sufficient percentage of the theoretical total extent of exposure.

The quality of log-linear regression (and, consequently, the reliability of the extrapolated PK parameters) should be demonstrated by a determination coefficient  $R^2 \ge 0.8$ . Individual extrapolated parameters, when considered unreliable, will be reported as NC (not calculated).

## 9.3 Safety assessments

Safety and general tolerability of the IMP will be based on TEAEs, physical examinations including body weight, vital signs and routine haematology, blood chemistry and urinalysis laboratory tests.

# 10 STATISTICAL METHODS

The data documented in this study and the parameters measured will be evaluated and compared using classic descriptive statistics, i.e. geometric mean (PK data only), arithmetic mean, SD, CV (%), minimum, median and maximum values for quantitative variables, and frequencies for qualitative variables.

Not available data will be evaluated as "missing values". The statistical analysis of demographic and safety data will be performed using SAS® version 9.3 (TS1M1) (13) or higher (the actual versions will be stated in the final report).

The statistical analysis of PK parameters will be performed using Phoenix WinNonlin® version 6.3 (12) or higher and SAS® version 9.3 (TS1M1) or higher.

#### 10.1 Analysis Sets

#### 10.1.1 Definitions

A subject will be defined as screened after the signature of the informed consent, regardless of the completion of all the screening procedures.

A subject will be defined as eligible if he/she meets all the inclusion/exclusion criteria. Otherwise he/she will be defined as a screen failure.

A subject will be defined as enrolled in the study if he/she is included into the interventional phase of the study. The enrolment will be performed through randomised allocation to one treatments sequence.

An eligible but not enrolled subject will be defined as a reserve.

A subject will be defined as randomised in the study when he/she is assigned to one randomised treatments sequence.

The following analysis sets are defined:

- Enrolled set: all enrolled subjects. This analysis set will be used for demographic, baseline and background characteristics
- Safety set: all subjects who receive at least one dose of the investigational medicinal products. This analysis set will be used for the safety analyses
- ➤ PK set: all randomised subjects who fulfil the study protocol requirements in terms of investigational medicinal product intake and have evaluable PK data readouts for the planned treatment comparisons, with no major deviations that may affect the PK results. This analysis set will be used for the statistical analysis of the PK results

Each subject will be coded by the CRO Biometry Unit as valid or not valid for the Safety set and the PK set. Subjects will be evaluated according to the treatment they actually receive.

## 10.1.2 Reasons for exclusion from the PK set before bioanalysis

Reasons for the exclusion of subjects from the PK set are the following:

- vomiting and diarrhoea after drug intake which could render the plasma concentrationtime profile unreliable
- intake of concomitant medications which could render the plasma concentration-time profile unreliable
- AEs which could render the plasma concentration-time profile unreliable
- ➤ administration errors which could render the plasma concentration-time profile unreliable
- > other events which could render the plasma concentration-time profile unreliable

If one of these events occurs, it will be noted in the CRF as the study is being conducted.

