## 4.2 Discussion of design

The study was designed in agreement with the EMA guideline "Guidance on the investigation of bioequivalence", CPMP/EWP/QWP/1401/98 Rev. 1 January 2010 (9). The well-known high variability of riluzole led to the choice of the replicate cross-over design as suggested by the current EMA guideline. According to the guideline, an enlargement of the acceptance interval for bioequivalence in terms of  $C_{max}$  is allowed up to 69.84-143.19% in relation to the actual intra-subject variability of riluzole  $C_{max}$  found in this study with the reference treatment, by keeping in consideration the favourable safety profile of the test formulation previously observed in 3 clinical studies. In detail, a  $C_{max}$  within-subject variability >30% was found in the previous pilot study and =32.66% in the previous bioequivalence study performed in USA (§ 1.4.2). According to the 2-arm cross-over study design, each randomised subject will be allocated to one of 2 sequences of IMP administrations in the 4 study periods according to a computer generated randomisation list (see § 8.1). Balance between the sequences will be made so that subjects have the same chances to be assigned to either sequence (either RTRT or TRTR in the 4 consecutive periods).

An open-label design will be used since the primary end-point of the study is based on objective measurements of riluzole in plasma and the outcome variables could not be influenced by the subjects or investigator being aware of the administered products. The bioanalysis will be performed under blinded conditions.

The washout period of 7 days was estimated to be adequate. Based upon a half-life of 12 h (Rilutek SmPC reference: 7), it is anticipated that minimal plasma levels would be achieved in 5 days thus allowing dosing every 7 days. Blood sampling time-points were selected on the basis of the known PK profile of riluzole and on the basis of previous Phase I studies of the same test formulation administered to healthy volunteers.

The dose for the present study was selected based on EMA Rilutek® European Public Assessment Report (EPAR) (10), which recommends a dose regimen of 50 mg (one film-coated tablet) twice a day in the common clinical practice. The dose of 50 mg is the minimal unit dose.

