#### 5.3.1 Not allowed treatments

No medication, including OTC and herbal remedies, will be allowed for 2 weeks before the start of the study and during the whole study duration.

Central nervous system depressants, including opioids, benzodiazepines, general anaesthetics and anticonvulsants, or CYP inhibitors, including cimetidine, fluoxetine, quinidine, erythromycin, ciprofloxacin, fluconazole, ketoconazole, diltiazem and antiretroviral agents, or

strong CYP inducers, including barbiturates, carbamazepine, glucocorticoids, phenytoin, St John's wort and rifampin, or hormonal oral or transdermal contraceptives will be forbidden for 30 days before study screening and during the whole study duration.

Implanted, injected, intravaginal or intrauterine hormonal contraceptives will be forbidden for 6 months before study screening and during the whole study duration.

Paracetamol will be allowed as therapeutic counter-measure for adverse events (AEs) according to the investigator's opinion.

The intake of any other medication will be reported as a protocol deviation. However, it will lead to subject's discontinuation from the study only if the investigator, together with the sponsor, considers it could affect the study assessments or outcome

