## 10.1.3 Reasons for exclusion from the PK set after bioanalysis

Exclusion of subjects on the basis of pharmacokinetic reasons is possible only for:

- > subjects with lack of any measurable concentrations or only very low plasma concentrations for the reference medicinal product. A subject is considered to have very low plasma concentrations if his/her AUC is less than 5% of the reference medicinal product geometric mean AUC (which should be calculated without inclusion of data from the outlying subject)
- > subjects with implausible concentrations (i.e. different from the known, expected concentration profiles) for the reference medicinal product. The exclusion of these subjects must be justified on the basis of sound scientific reasons and mutually agreed between the CRO and the Sponsor
- ➤ subjects with non-zero baseline concentrations > 5% of Cmax

The samples from the subjects excluded from the PK set should still be assayed and the results listed. Subjects should not be excluded from the PK set if the  $AUC_{0-t}$  covers less than 80% of the  $AUC_{0-\infty}$ .

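### PK-set exclusion is worded by subject while most pre-bioanalysis triggers concern one period, so, read as written, one unreliable profile can remove up to three valid ones; the cost is modest precision.

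*Protocol*

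**What the plan says.** Protocol 10.1.1 makes PK-set membership a property of the subject: "Each subject will be coded by the CRO Biometry Unit as valid or not valid for the Safety set and the PK set". Protocol 10.1.2 keeps that unit ("Reasons for the exclusion of subjects from the PK set are the following"), but its triggers are events that spoil one concentration-time curve, for example "AEs which could render the plasma concentration-time profile unreliable". The list ends with an open category of other events. SAP 8.2.1 and 8.2.1.1 repeat this text, and SAP 1.1 declares no change from the protocol and its amendment. (The amendment is not among the documents reviewed; the SAP postdates it.)

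Neither document says what happens to a subject's other periods, or how many test (T) and reference (R) profiles a subject needs. The nearest statement is the membership condition in Protocol 10.1.1, that subjects "have evaluable PK data readouts for the planned treatment comparisons". The status of someone who leaves early with one valid T and one valid R profile is also open.

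In the SAP shells, Listing 16.2.4.2 has one PK-set flag per subject. Listing 16.2.6.1 is laid out by period but restricted to PK-set subjects. Table 14.1.1.2 counts the PK set separately for T, R and overall.

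**The concern.** Each subject contributes two T and two R profiles (Protocol 3.1.2). If one is unreliable and the subject is coded not valid, up to 4 - 1 = 3 valid profiles go with it. The planned model in Protocol 10.6.2, with treatment, period, sequence and subject within sequence as fixed effects, can use those three. When the bad profile is a T profile, both R values that feed the reference within-subject SD (SWR), and hence the widened Cmax limits, are lost too.

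At stake are some precision on the T/R ratio and some replicates for SWR. Two analysts could also build different PK sets from the same data, because the choice rests on a judgement that is not written down. The margin is thin on paper: Protocol 10.2 enrols 54 to have 52 completers, and Protocol 14.4.2 does not replace withdrawals.

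**Working it through.** **Inputs.** Protocol 10.2: Cmax ratio 1.11, CV 0.3266, limits 0.80-1.25, each one-sided test at 5%, 52 completers of 54 enrolled. Protocol 8.2: sequences RTRT and TRTR. The number of affected subjects, k, is assumed, because the documents give no rate of unusable profiles.

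**The plan's own figure.** Protocol 10.2 does not state its variance formula. Taking the log-scale SD as the CV itself, SE² = 1.1 × CV²/N and 3N - 5 degrees of freedom reproduces all its Cmax totals: 26, 46, 52 and 126 for ratios 1.05, 1.10, 1.11 and 1.1582. At N = 52, SE = √(1.1 × 0.3266²/52) = 0.0475 and power is 80.1%.

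**Model for the comparison.** Log-scale within-subject SD σ = √ln(1 + 0.3266²) = 0.318, the same for both products. With subject, period and treatment fixed and N complete subjects, SE = σ/√N. For N = 54 this is 0.318/√54 = 0.0433, with 158 degrees of freedom and 86.1% power. Power is the probability that the 90% CI lies inside the limits, integrated over the residual variance.

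**What one bad profile costs.** A complete subject's T minus R contrast has variance σ²(1/2 + 1/2) = σ². With one profile missing it is σ²(1/2 + 1) = 1.5σ², so the subject keeps 1/1.5 = 2/3 of its information. With k affected subjects of 54, effective N is 54 - k under subject-level exclusion and about 54 - k/3 under period-level exclusion. The full design matrix agrees.

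| k of 54 | Effective N, subject vs period | SE larger by | Fixed-limit power, subject vs period |
|---|---|---|---|
| 2 | 52.0 vs 53.3 | √(53.33/52) - 1 = 1.3% | 84.9% vs 85.7% |
| 6 | 48.0 vs 52.0 | √(52/48) - 1 = 4.1% | 82.3% vs 84.9% |
| 10 | 44.0 vs 50.7 | √(50.67/44) - 1 = 7.3% | 79.3% vs 84.1% |

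**Under the plan's own variance convention**, levels are lower. For 1 affected subject of 52, power is 79.4% vs 79.9%; for 4 of 52 it is 77.2% vs 79.2%.

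**Early leavers.** Suppose the two non-completers the plan allows for leave after period 2. Each has one T and one R, variance 2σ², and so half a subject's information. Leaving both out makes the SE √(53/52) - 1 = 1.0% larger (84.9% vs 85.5%). If they leave after period 3, the figures are 1.3% and 84.9% vs 85.7%.

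**With the planned widening of the Cmax limits**, levels are higher: about 92%, 90% and 88% for 52, 48 and 44 complete subjects. In simulation (30,000 trials per rate), assumed rates of 1% and 3% bad profiles gave 92.2% vs 92.7% and 90.2% vs 92.0%. The simulation error is about √(0.92 × 0.08/30,000) = 0.16 points per figure, so gaps of a few tenths should not be read closely.

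**The case against.** The strongest reply is that the documents are ambiguous and do not order the loss of valid data. Four points support it.

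- The condition that subjects "have evaluable PK data readouts for the planned treatment comparisons" can be met with one T and one R profile.
- The opening of Protocol 10 treats unavailable data as missing values.
- Table 14.1.1.2 counts the PK set by treatment, which would add little if membership were always all or nothing.
- Listing 16.2.6.1 could show a subject with one row absent.

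This stands in part. A reader might infer that the plan prescribes discarding three good profiles, and the text does not go that far. But none of the four states a period-level rule. The missing-values sentence concerns data that are not available, not an available profile judged unreliable, and the single code per subject points the other way.

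Second, not every trigger is confined to one period. CNS depressants, CYP inhibitors and strong CYP inducers "will be forbidden for 30 days before study screening and during the whole study duration", against dosing that may be seven days apart, so one intake may affect several profiles. That stands, and fewer than three valid profiles are then lost.

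Third, it may seem natural to extend the point to the post-bioanalysis rules in Protocol 10.1.3. The documents give little reason to. The pre-dose rule ("subjects with non-zero baseline concentrations > 5% of" Cmax) should almost never fire: seven days at the stated 12 h half-life is 14 half-lives, leaving 2⁻¹⁴ = 0.006%. The low-exposure rule ("if his/her AUC is less than 5% of the reference medicinal product geometric mean AUC") means below about 0.05 × 714.48 = 35.7 or 0.05 × 807.545 = 40.4 ng·h/mL on the earlier studies' reference means. Those rules are deliberately narrow, and loosening them would allow single reference profiles to be removed once concentrations are known.

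**Conclusion.** The point holds as a matter of wording with a small cost. For the pre-bioanalysis triggers, the text as written excludes subjects where excluding periods would keep usable data.

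The effect is on precision only. The same events trigger either rule, and the choice between them does not by itself shift the T/R estimate or raise the type I error. At the plan's own allowance of two lost subjects, the difference is under one power point; at six affected subjects it is 2.6 points (84.9 - 82.3). Both use fixed limits, equal within-subject variance for T and R, a true ratio of 1.11 and assumed event counts.

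A reader might infer from the 79.3% at ten affected subjects that the study risks being underpowered. The documents do not support that. They give no such event rate, the figure ignores the planned widening, and with widening even 44 complete subjects give about 88%. This is an improvement to consider, not a defect that threatens the conclusion.

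**What to change.** In Protocol 10.1.1-10.1.2 and SAP 8.2.1-8.2.1.1, for the pre-bioanalysis triggers and decided before concentrations are known:

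1. Exclude only the period or periods whose profile is judged unreliable.
2. Keep in the T/R comparison every subject with at least one evaluable T and one evaluable R profile, including early leavers.
3. Estimate SWR from subjects with two evaluable R profiles.
4. Add a per-period PK flag to SAP Listing 16.2.4.2.

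Leave Protocol 10.1.3 as it is. The cost is a text edit, made by protocol amendment or declared in SAP 1.1, with no extra subjects or samples. The data become slightly unbalanced, which the planned fixed-effects model handles. Whether a profile is unreliable remains a judgement, but its consequence would be fixed in advance.

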## 10.1.3 Reasons for exclusion from the PK set after bioanalysis

Exclusion of subjects on the basis of pharmacokinetic reasons is possible only for:

- > subjects with lack of any measurable concentrations or only very low plasma concentrations for the reference medicinal product. A subject is considered to have very low plasma concentrations if his/her AUC is less than 5% of the reference medicinal product geometric mean AUC (which should be calculated without inclusion of data from the outlying subject)
- > subjects with implausible concentrations (i.e. different from the known, expected concentration profiles) for the reference medicinal product. The exclusion of these subjects must be justified on the basis of sound scientific reasons and mutually agreed between the CRO and the Sponsor
- ➤ subjects with non-zero baseline concentrations > 5% of Cmax

The samples from the subjects excluded from the PK set should still be assayed and the results listed. Subjects should not be excluded from the PK set if the  $AUC_{0-t}$  covers less than 80% of the  $AUC_{0-\infty}$ .

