8.6 PK and Palatability analysis

The date/time and score of palatability (for test only) will be listed (Listing 16.2.6.2) and summarised in tables of frequency (Table 14.2.4.2) on the safety set.

The PK analysis will be performed on the subjects included into the PK Set. Subjects will be analysed according to the treatment they actually received.

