8.6.3 Statistical comparison of pharmacokinetic parameters

According to the current European Guideline on the Investigation of Bioequivalence (3), plasma riluzole AUC_{0-t} , $AUC_{0-\infty}$ and C_{max} will be analysed using analysis of variance (ANOVA) (Table 14.2.3.1).

A mixed linear model will be used to make statistical inferences about the values of C_{max} and AUC_{0-t}. In order to correctly assume normality and homoscedasticity, the data will be transformed prior to analysis using a neperian logarithmic transformation in compliance with the EMA guideline.

The 90% CI of the ratio of the population means (test/reference), for the parameters under consideration will be calculated. This method is equivalent to the corresponding two one-sided test procedure with the null hypothesis of bioequivalence at the 5% significance level.

- The statistical analysis will take into account treatment, period, sequence and subject within sequence as fixed effects.
- Acceptance criterion for bioequivalence in terms of extent of absorption (AUC_{0-t} as primary variable and AUC_{0-∞} as secondary variable) will be that the 90% CI of this ratio has to lie within the range 80.00-125.00%.
- Due to the replicate design of the study, if the within-subject variability (CV_{WR} %) of C_{max} of plasma riluzole after administration of the reference formulation is >30%, the reference-scaled BE approach will be used. Bioequivalence acceptance range for C_{max} will be widened, in compliance with the guideline, as exemplified in Table 8.9.3.1.
- $CV_{WR}\%$ will be calculated by applying the formula $CV_{WR}(\%) = 100\sqrt{e^{S^2_{WR}} 1}$, where S^2_{WR} is the within-subject variation plasma riluzole after administration of the reference formulation only.
- The extent of the widening will be defined on the basis of the within-subject variability actually observed in the study according to $[U, L] = \exp [\pm k \cdot S_{WR}]$, where U is the upper limit of the acceptance range, L is the lower limit of the acceptance range, k is the regulatory constant set to 0.760 and S_{WR} is the within-subject standard deviation of the log-transformed values of C_{max} of plasma riluzole after administration of the reference formulation.

CV _{WR} %*	Lower Limit	Upper Limit
30	80.00	125.00
35	77.23	129.48
40	74.62	134.02
45	72.15	138.59
≥50	69.84	143.19

Table 8.9.3.1 Examples of widened bioequivalence acceptance limits of C_{max} according to its actual CV_{WR}

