Table 14.2.2.1 - Riluzole plasma PK parameters - PK Set

Investigational Medicinal Product: Rilutek®, 50 mg riluzole tablets (R)

Statistics	C _{max} (ng/mL)	t _{max} (h)	AUC _{0-t} (h*ng/mL)	AUC _{0-inf} (h*ng/mL)	t½ (h)	λz (1/h)
N	XX	XX	XX	XX	XX	XX
Geo.Mean	XXX.XX	XXX.XX	XXX.XX	XXX.XX	XXX.XX	XXX.XX
Mean	XXX.XX	XXX.XX	XXX.XX	XXX.XX	XXX.XX	XXX.XX
SD	XXX.XX	XXX.XX	XXX.XX	XXX.XX	XXX.XX	XXX.XX
CV%	XXX.XX	XXX.XX	XXX.XX	XXX.XX	XXX.XX	XXX.XX
Min	XXX.XX	XXX.XX	XXX.XX	XXX.XX	XXX.XX	XXX.XX
Median	XXX.XX	XXX.XX	XXX.XX	XXX.XX	XXX.XX	XXX.XX
Max	XXX.XX	XXX.XX	XXX.XX	XXX.XX	XXX.XX	XXX.XX

Source: Listing 16.2.6.1 - Riluzole plasma PK parameters Program: pk-analysis\k344-tlf.sas

Statistical analysis plan CRO-PK-20-344 Sponsor code Z7251J01 Riluzole orodispersible film replicate bioavailability Final version 1.0, 31MAY21

Analysis	Dependent Variable	Comparison	Point Estimate	90% Confidence Interval Lower Limit	90% Confidence Interval Upper Limit	Effect	p Value
ANOVA	Ln(AUC _{0-inf})	T vs R	XXX.XX	XXX.XX	XXX.XX		
						Sequence	X.XXXX
						Treatment	X.XXXX
						Period	X.XXXX
ANOVA	Ln(AUC _{0-t})	T vs R	XXX.XX	XXX.XX	xxx.xx		
						Sequence	XXXXX
						Treatment	X.XXXX
						Period	X.XXXX
ANOVA	Ln(C _{max})	T vs R	XXX.XX	XXX.XX	XXX.XX		
						Sequence	X.XXXX
						Treatment	X.XXXX
						Period	X.XXXX

Table 14.2.3.1 - Statistical analysis on riluzole plasma PK parameters - PK set

T: Riluzole 50 mg orodispersible film (T)

R: Rilutek[®], 50 mg riluzole tablets (R) _

Program: pk-analysis\k344-tlf.sas

Statistical analysis plan CRO-PK-20-344 Sponsor code Z7251J01 Riluzole orodispersible film replicate bioavailability Final version 1.0, 31MAY21

Table 14.2.3.2 - Within-subject variability of C_{max} (after administration of the reference formulation) - PK Set

AINGR	Dependent Variable	${S^2}_{WR}$	Within-subject variability CV _{WR} (%)
Riluzole	Ln(C _{max})	XXX.XXX	XX.XX

Note: CV_{WR} % was calculated by applying the formula 100*sqrt[exp(S^2_{WR})-1] Program: pk-analysis\k344-tlf.sas

Statistical analysis plan CRO-PK-20-344 Sponsor code Z7251J01 Riluzole orodispersible film replicate bioavailability Final version 1.0, 31MAY21

Table 14.2.3.3 - Non-parametric Friedman test on t_{max} and $t_{1/2}$ - PK set

Analysis	Dependent Variable	Comparison	p Value
Friedman	t _{max}	T vs R	X.XXXX
	t _{1/2}	T vs R	X.XXXX

Program: pk-analysis\k344-tlf.sas

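### Could removing subjects with implausible reference profiles after bioanalysis bias the bioequivalence verdict, given that no text puts the decision before the T/R result?

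*Protocol*

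**What the plan says.** Protocol 10.1.3, repeated in SAP 8.2.1.2, opens with a restriction: "Exclusion of subjects on the basis of pharmacokinetic reasons is possible only for" three groups. These are subjects with absent or very low reference concentrations (AUC under 5% of the reference geometric mean), "subjects with implausible concentrations (i.e. different from the known, expected concentration profiles) for the reference medicinal product", and subjects with pre-dose levels above 5% of Cmax. The middle group has no number. It has a condition instead: "The exclusion of these subjects must be justified on the basis of sound scientific reasons and mutually agreed between the CRO and the Sponsor".

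On who decides, Protocol 10.1.1 says "Each subject will be coded by the CRO Biometry Unit as valid or not valid for the Safety set and the PK set", and SAP 1 gives the statistical analysis to the same unit. On the data used, SAP 8.6 says "The PK analysis will be performed on the subjects included into the PK Set". Both relevant shells, Table 14.2.3.1 (treatment comparison) and Table 14.2.3.2 (reference within-subject variability), are on that set alone. For Cmax, SAP 8.6.3 adds that "The extent of the widening will be defined on the basis of the within-subject variability actually observed in the study".

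Excluded subjects are not hidden. Protocol 10.1.3 requires their samples to be assayed and the results listed, and SAP 8.4.3 lists each exclusion with its reason. The PK-parameter listing (16.2.6.1) does cover PK-set subjects only.

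**The concern.** Nothing supplied dates the decision. Events before bioanalysis have to be entered in the CRF as they happen (Protocol 10.1.2), but this ground has no equivalent rule. The study is open-label. Blinding of the assay (Protocol 4.2) binds the laboratory, not the CRO and sponsor, who decide. Finalising the SAP before database lock fixes its text, not the list of exclusions.

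A removed subject can shift the Cmax ratio and also the reference SD that sets the Cmax limits. If the choice were made knowing the T/R result, the 5% error rate would not be protected. Cmax may also be near the boundary, since the earlier bioequivalence study gave a ratio of 1.1582 (Protocol 10.2). With no run including the excluded subjects, a reader would have to rebuild that result from the concentration listing.

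**Working it through.** **1. Inputs.** N = 52, 26 per sequence (Protocol 10.2); CVWR 32.66% for Cmax (Table 1.4.2.1); k = 0.760 and a cap of 143.19% (Protocol 10.6.2, Table 10.6.2.1); 90% CI. Assumed: the same CV for the test product, and a between-subject log SD of 0.4.

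**2. The plan's own limits.** sWR = √ln(1 + CV²). At CV 35%, sWR = 0.3399 and exp(±0.760 × 0.3399) gives 77.23-129.48%, as in Table 10.6.2.1. At 32.66%, sWR = 0.3184 and the upper limit is exp(0.760 × 0.3184) = 1.274. The boundary ratios to test are therefore 1.25 (fixed limits) and 1.274 (widened).

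**3. What one profile can do.** SE = 0.3184 × √[0.25 × (1/26 + 1/26)] = 0.0442, with 3 × 52 − 4 = 152 df. At an observed ratio of 1.1582 the 90% CI is 1.077-1.246. One reference Cmax 5-fold too low shifts the log ratio by (ln 5)/2/26/2 = 0.0155, a factor of 1.016. That takes the upper bound to about 1.27 before any change in SE, so it would cross 1.25 if the limits were not widened. The stake is real if such a profile occurs.

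**4. Does the exclusion itself bias the test?** In 40,000 simulated trials per case, the three subjects whose reference mean lies furthest from the trial average, in either direction, are open to exclusion. Chosen with sight means the trial passes if dropping any subset of the three, or none, gives a pass.

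| Case | Nobody dropped | All three dropped unseen | Chosen with sight |
|---|---|---|---|
| Fixed limits, ratio 1.25 | 5.0% | 5.3% | 7.6% |
| Widened limits, ratio 1.274 | 7.1% | 7.3% | 10.2% |
| Widened limits, ratio 1.1582 (pass rate) | 69.0% | 66.9% | 75.1% |

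The 7.1% comes from the widening rule, not from exclusions. Dropping without sight is close to neutral.

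**5. Are those candidates implausible?** No aberrant value was put into these data. The three candidates lie a median of 3.1-, 2.65- and 2.4-fold from the geometric mean, which is an ordinary lognormal tail. The table below requires a minimum distance before a subject can be a candidate (up to three, chosen with sight; 12,000 trials, Monte Carlo SE about 0.2 point).

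| Candidate must lie beyond | Fixed, ratio 1.25 (baseline 5.0%) | Widened, ratio 1.274 (baseline 6.8%) |
|---|---|---|
| 3-fold | 5.7% | 7.6% |
| 4-fold | 5.1% | 6.9% |
| 5-fold | 5.0% | 6.8% |

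A subject beyond 4-fold occurs in 11% of trials, and beyond 5-fold in 2%.

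**6. The assumed SD.** The pilot study (Table 1.4.1.1) gives a reference Cmax CV of 48.32% overall and 32.13% within subject. On a lognormal approximation the between-subject SD is √[ln(1 + 0.4832²) − ln(1 + 0.3213²)] = √(0.2098 − 0.0982) = 0.33. At 0.33 with fixed limits, the baseline of 4.8% becomes 5.1% beyond 3-fold and 4.9% beyond 4-fold.

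**7. Would the inclusive run inform?** Suppose one reference Cmax is 10-fold too low (assumed), the ratio is 1.274 and the limits are widened. False bioequivalence is 15.6% with the subject kept and 6.7% with the subject excluded. The median upper limit is 134% against 127%, because the error inflates sWR. When the value is truly aberrant, the run with the subject included is the less reliable one.

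**The case for a change.** The strongest case is that the existing safeguards govern why a subject leaves, not when, and that one unit both codes the set and runs the analysis. The with-sight figures in step 4 are then what an unscrupulous reading allows. Removing the three subjects with the lowest reference relative to their own test mean would take the error to about 21%. Even without sight, one-sided use matters: at fixed limits and a 5.1% baseline, always dropping the lowest one, two or three on reference gives 6.2%, 7.6% or 8.8%. If one reference Cmax really is 5-fold too low or too high, the verdict at 1.1582 differs with and without the subject in 9.5% or 20.7% of trials. Two SAP sentences would settle both matters.

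The timing gap stands as an omission. The figures carry less weight:

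- The 21% needs selection on the test profile, which this ground does not allow.
- The one-sided figures need low profiles to be removed in every trial while high ones are kept. The wording covers departures in either direction, and each case needs a stated reason and is listed.
- The 9.5% and 20.7% are conditional on an error whose size is assumed and whose frequency no document gives.

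The sentences also have drawbacks. Confining the decision to reference profiles could prevent a look at the test profiles to detect a sample swap. Freezing before sWR is computed protects only partly, because paired reference profiles already show it informally.

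**Conclusion.** No change follows. This is missing detail that analysts fill sensibly. An analysis specified on the PK set presupposes that membership has been settled, and coding it before the comparison is ordinary practice. Followed as written, the rule gives a sound result: blind exclusion moves false bioequivalence from 5.0% to 5.3%. Even result-driven use adds about 0.7 point at fixed limits and 0.8 point under the widened rule if candidates must lie beyond 3-fold, and about nothing beyond 4-fold. The 7.6% and 10.2% figures are bounds that ignore the requirement of implausibility.

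An inclusive run would be supportive only. It leaves the primary result as it is, and the listed concentrations let a reader rebuild it.

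This rests on a lognormal model with equal variability for both products, a between-subject log SD of 0.33-0.4, and distance from the mean as a stand-in for implausibility; profile shape is not modelled. The protocol amendment cited in the SAP was not available, although SAP 1.1 reports no departure from it.
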